**Interventions**

Patients included in the study will be randomly distributed in a 1:1 ratio to receive the two treatment regimens.

## 1. Initial assessment and follow-up

Initial medical assessment including:

1. Complete medical history
2. Hepatic ultrasound showing evidence of hepatic steatosis. The degree of hepatic steatosis will be determined according to Hamaguchi score ( $\geq 3$  points) classifying it as follows: absent (0 points), mild (1 point), moderate (2 points) and severe (3 points). This scoring system has a maximum sum of 6 points and considers hepatorenal echo contrast, hepatic brightness, deep attenuation and vascular visualization with a specificity of 100% and sensitivity of 91.7%.
3. The risk of fibrosis will be determined according to FIB-4, NAFLD score or APRI. FIB-4 is considered high risk of fibrosis score  $\geq 3.25$ , indeterminate 1.45-3.25 and absent  $\leq 1.45$ ; in NAFLD score high risk with  $\geq 0.675$ , indeterminate -1.455 to 0.675 and absent  $\leq -1.455$ ; in APRI high risk of significant fibrosis with score  $\geq 1.5$ , indeterminate 0.5-1.5 and absent  $\leq 0.5$ .
4. Transitional liver elastography with FibroScan® will be performed at baseline, 12 and 24 weeks follow-up to estimate hepatic fatty infiltration according to the controlled attenuation parameter (CAP) and hepatic stiffness in kilopascals (kpa). Considering fibrosis stages the following cut-off points F0  $\leq 6.4$ kpa, F1 6.5 to 6.9 kpa, F2 7 to 8.6kpa, F3 8.7 to 10kpa, F3-F4 10.1 to 15 kpa and F4  $\geq 15$ kpa. For hepatic fatty infiltration is considered by CAP S0  $\leq 247$ , S1 between 248 to 267, S2 268 to 279 and S3  $\geq 280$ . 10 representative valid measurements with success rate (IQR) 30% are considered. All measurements will be taken by the same operator.
5. At baseline, 12 and 24 weeks follow-up the following laboratory studies will be performed: blood biometry, blood chemistry, liver function tests, lipid profile and C-reactive protein, serum insulin, HOMA calculation.
6. The study of viral hepatitis type B and C will be performed at the beginning of the study.

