### **Specific Objectives:**

- To assess the effects of administering alpha-lipoic acid and Silybum marianum (LUDLEV® 300 mg/46.2 mg) in combination with a Mediterranean diet versus placebo plus a Mediterranean diet on fibrosis and steatosis in patients with MAFLD after 12 weeks of treatment.
- To evaluate changes in fibrosis measured by kPa using FibroScan® elastography after 12 and 24 weeks of administering alpha-lipoic acid and Silybum marianum (LUDLEV® 300 mg/46.2 mg) every 12 hours in combination with a Mediterranean diet, compared to placebo plus a Mediterranean diet in patients with MAFLD.
- To assess changes in the controlled attenuation parameter (CAP) measured by FibroScan® elastography after 12 and 24 weeks of administering alpha-lipoic acid and silybum marianum (LUDLEV® 300 mg/46.2 mg) every 12 hours in combination with a Mediterranean diet, compared to placebo plus a Mediterranean diet in patients with MAFLD.
- To evaluate biochemical improvement after 12 and 24 weeks of administering alpha-lipoic acid and Silybum marianum (LUDLEV® 300 mg/46.2 mg) every 12 hours in combination with a Mediterranean diet, compared to placebo plus a Mediterranean diet in patients with MAFLD.
- To assess weight loss and changes in body composition after 12 and 24 weeks of administering alpha-lipoic acid and Silybum marianum (LUDLEV® 300 mg/46.2 mg) every 12 hours in combination with a Mediterranean diet, compared to a Mediterranean diet alone in patients with MAFLD.

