### **Inclusion criteria:**

- Subjects treated at the Instituto de Investigaciones Médico-Biológicas de la Universidad Veracruzana, diagnosed with fatty liver.
- Willingness to voluntarily participate in the study and signing of informed consent.
- Age over 18 years, both sexes.
- Patients with evidence of hepatic steatosis and overweight or obesity.
- Patients with evidence of hepatic steatosis, diabetes mellitus, and overweight or obesity.
- Patients with evidence of steatosis plus metabolic risk abnormalities (waist circumference >102 cm in men, 88 cm in women, blood pressure >130/85 mmHg or on specific treatment, triglycerides >150 mg/dL or on specific treatment, HDL cholesterol <40 mg/dL in men, <50 mg/dL in women or on specific treatment, HOMA-IR >2.5, CRP >2 mg/dL, or prediabetes defined by fasting plasma glucose 100-125 mg/dL, 2-hour postload glucose 140-199 mg/dL, or HbA1c between 5.7% and 6.4%).
- Agree not to start a diet program during the study.
- Agree not to change their current exercise plan during the study.

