### **Exclusion criteria:**

- Patients who meet diagnostic criteria for MAFLD with normal weight.
- Patients with terminal illness, cancer, or end-stage renal disease on renal replacement therapy.
- Pregnant women.
- Patients who are unable to understand or follow the study protocol.
- Sensitivity to the components of the formula.

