**Elimination criteria:**

- Patients who do not comply with the follow-up time and drug administration.
- Patients who do not comply with proper drug intake.
- Patients with intolerance or severe adverse effects to the components of the drug.
- Patients who are unable to undergo FibroScan® examination due to technical limitations.

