#### **4. Follow-up and surveillance**

1. Physical activity: It will be evaluated by means of the international physical activity questionnaire (IPAQ) that categorizes the levels of physical activity in: low (category 1), moderate (category 2) and high (category 3) according to the intensity, frequency and duration of the training. The recommendation will be made not to modify the usual training plan.
2. Nutritional plan: The monitoring will be carried out in a personalized way through a monthly face-to-face nutritional consultation.
3. Pharmacological treatment: The adherence to the pharmacological treatment will be monitored through a monthly telephone interview. Telephone assistance will be available to resolve doubts and report adverse effects.

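### HOMA is calculated in every patient at three visits although insulin users may enrol and insulin use is not recorded in follow-up, so in those users HOMA is not a valid measure of insulin resistance

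*Protocol*

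**What the plan says.** The Protocol, Initial assessment and follow-up, item 5, sets the laboratory schedule: "At baseline, 12 and 24 weeks follow-up the following laboratory studies will be performed". The list closes with "lipid profile and C-reactive protein, serum insulin, HOMA calculation". No subgroup is exempted and no formula for HOMA is given.

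The Inclusion criteria name as one entry category "Patients with evidence of hepatic steatosis, diabetes mellitus, and overweight or obesity", with no condition on how the diabetes is treated. The Exclusion criteria cover normal weight, serious illness ("Patients with terminal illness, cancer, or end-stage renal disease on renal replacement therapy"), pregnancy, inability to follow the protocol and sensitivity to the product. The Elimination criteria concern follow-up, intake of the study drug ("Patients who do not comply with proper drug intake"), intolerance and FibroScan feasibility. Neither list mentions insulin or any other antidiabetic drug.

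Under Follow-up and surveillance, the only item on medication is "The adherence to the pharmacological treatment will be monitored through a monthly telephone interview", which reads as adherence to the study product. One specific objective is "To evaluate biochemical improvement after 12 and 24 weeks" of treatment. It does not name HOMA.

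**The concern.** HOMA combines glucose with serum insulin and treats the insulin as the patient's own secretion. Where part of the measured insulin has been injected, that reading fails: HOMA can rise or fall with the injected amount while the patient's own insulin does not change. Both arms follow a low-calorie diet for 24 weeks, a setting in which insulin doses may plausibly change, and a dose change would then appear as a change in HOMA.

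At stake is the interpretation of one secondary laboratory measure. It has some weight here because the Background cites reduced insulin resistance as an effect of alpha-lipoic acid, and HOMA is the only index of insulin resistance in the panel. A difference between arms could easily be taken as support for that mechanism. With 40 to 50 patients, a few uninterpretable values can matter.

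**Working it through.** The plan states no figure on this point, so there is none to reproduce. The check has two parts.

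**1. Does the text let insulin users into the HOMA data?**
- HOMA is scheduled at three visits for all patients (Initial assessment and follow-up, item 5).
- Diabetes with overweight or obesity is an entry category, with no treatment condition (Inclusion criteria).
- No insulin criterion appears in the Exclusion or Elimination criteria, both read in full.
- Baseline insulin use would ordinarily appear in the medical history (same section, item 1). Nothing provides for noting a new start or a dose change at 12 or 24 weeks (Follow-up and surveillance).
- The section on analysis of the results does not restrict HOMA to any subset.

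So insulin users can enter, their HOMA is calculated, and changes in their insulin use are not scheduled to be captured.

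**2. How far could HOMA move?** The usual form is assumed, because the Protocol gives none: HOMA = glucose (mg/dL) × insulin (µU/mL) / 405. All insulin and glucose values below are assumptions.

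Own fasting insulin is held at 10, and injected insulin seen by the assay adds 0, 10, 30 or 60:

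| Glucose | +0 | +10 | +30 | +60 |
|---|---|---|---|---|
| 100 | 2.47 | 4.94 | 9.88 | 17.28 |
| 130 | 3.21 | 6.42 | 12.84 | 22.47 |
| 160 | 3.95 | 7.90 | 15.80 | 27.65 |

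For scale, the HOMA-IR threshold in the Inclusion criteria is 2.5.

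*Effect on an arm mean.* At glucose 150, measured insulin of 15 gives 150 × 15 / 405 = 5.56, and 60 gives 150 × 60 / 405 = 22.2. One such patient among 20 moves the mean by (22.2 − 5.56) / 20 = 0.83.

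*Effect on change from baseline.*
- Injected contribution of 30 at both visits, glucose steady at 130: 12.84 − 12.84 = 0, so the inflation cancels.
- Injected contribution of 30 at both visits, glucose falling from 130 to 100: the inflation is 12.84 − 3.21 = 9.63 at the first visit and 9.88 − 2.47 = 7.41 at the second. It largely cancels, leaving 9.63 − 7.41 = 2.22.
- Injected contribution falling from 30 to 10, glucose steady at 130: 6.42 − 12.84 = −6.42, an apparent improvement with no change in the patient's own insulin.

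*How many patients.* The Protocol does not say. If 5% to 20% of 50 used insulin (assumption), that would be 2.5 to 10, or about 3 to 10 patients. None is also possible.

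**The case against.** The strongest reply is that this belongs in a statistical analysis plan. Item 5 is a list of tests. It fixes no analysis set, and a SAP that is not shown could restrict HOMA using the baseline medical history. That is partly right: the restriction could be written there. But the Protocol fixes the calculation for all patients and the data collected in follow-up, and a SAP cannot use insulin starts or dose changes that no one was asked to record.

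Other parts of the reply stand and limit the point:
- HOMA is not named in the biochemical objective. That it will be compared between arms is a reasonable inference, not a statement in the text.
- Continuous variables are to be summarised according to their distribution. A skewed HOMA would point to a median, which a few extremes barely move. The sentence on tests is unclear, so neither a comparison of means nor a rank test is assured.
- Stable injected insulin largely cancels in change from baseline.
- In a randomised, double-blind trial, a chance imbalance in insulin users mainly adds noise. Systematic bias would need insulin changes that differ between arms for reasons other than insulin sensitivity, and nothing in the Protocol shows this.

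A reader might also infer that HOMA in these patients simply tracks the injected dose. That is too absolute: the distortion depends on insulin type, assay cross-reactivity and injection timing, none of which is given.

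**Conclusion.** The point holds for one secondary laboratory measure. As written, the plan produces HOMA values in insulin users that cannot be interpreted as insulin resistance, and it schedules no follow-up record by which changes in insulin use could be recognised. This rests on how HOMA is built and on the absence of any insulin criterion or follow-up record in the sections listed above.

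The size cannot be established from the Protocol. The number of insulin users is unknown, and the shift of about 0.8 in an arm mean depends on assumed insulin and glucose values and on a mean being used at all.

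A reader might infer that the trial's main result is compromised or that one arm is favoured. The Protocol supports neither. The Hypothesis rests on stiffness in kPa and on CAP, which HOMA does not enter, and no direction of bias can be shown.

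**What to change.** In Initial assessment and follow-up, item 5, add that:
- insulin use is recorded at baseline, 12 and 24 weeks;
- HOMA is compared between arms only in patients not using insulin at baseline, a subset fixed before randomisation so that the randomised comparison is preserved;
- the number left out is reported per arm, and glucose is analysed in all patients;
- new insulin starts are reported by arm and handled in a sensitivity analysis, giving HOMA with and without the values after the start.

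The main analysis should not set HOMA to missing after a new start. A start is a post-randomisation event that is likely linked to worsening glycaemia, so dropping those values could remove patients selectively and unequally between arms.

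The cost is that HOMA rests on slightly fewer patients and that insulin use must be noted at two follow-up visits. No eligibility, dose or treatment rule changes.

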## **2. Nutritional assessment and follow-up**

The nutritional assessment will consist of:

1. Nutritional medical history: anthropometric measurements, basic electrical impedance and nutritional diagnosis.
2. A diet plan will be established with a Mediterranean style diet according to nutritional diagnosis and sex (caloric plans of 1400, 1500, 1600 or 1700 kcal/day). The composition of the diet is designed to receive 20% protein, 50% carbohydrates, 15% monounsaturated fats, 10% polyunsaturated fats, 5% saturated fats, less than 250 mg/day cholesterol and 20-30 g/day fiber.
3. Subsequent nutritional follow-up appointments: will be carried out in person on a monthly basis for 24 weeks.
4. Anthropometric measurements and basic electrical impedance at 12 and 24 weeks of follow up.
5. Test of adherence to the dietary plan at 12 and 24 weeks of follow-up.

## **3. Randomization by groups**

1. Patients will be randomly distributed by systematic sampling into 2 groups (A and B).
  - Group A will receive placebo in combination with a personalized low-calorie Mediterranean diet adjusted for age and sex (between 1400 to 1700 kcal/day) for 24 weeks.
  - Group B will receive alpha-lipoic acid ethyl esters and silybum marianum (LUDLEV® 300 mg/46.2 mg) every 12 hours in association with a personalized low-calorie Mediterranean diet adjusted for age and sex (between 1400 to 1700 kcal/day) for 24 weeks.

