## **METHODOLOGY**

### **Research Design**

**Study type:** Randomized, controlled, double-blind clinical trial.

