### **Population Definition**

Patients regularly attending the outpatient clinic of the Gastroenterology Department of the Instituto de Investigaciones Médico-Biológicas de la Universidad Veracruzana, diagnosed with MAFLD.

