**Sample size calculation**

It is calculated based on the previous study by Martinez Rodriguez et al.( Clinical and Experimental Pharmacology Clin Exp Pharmacol 2014, 5:1) where forty patients with NAFLD were randomized into two groups to receive metformin 1500 mg q.a.d. or metformin 1500 mg q.a.d. + (15 mcg)-methionine (3 mg)-alpha lipoic acid (200 mg) group for 24 weeks, and showed a 70% versus 15% decrease in ultrasound-graded steatosis ( $p < 0.001$ ) in patients receiving alpha lipoic acid. Taking into account this difference in proportions, considering a power of 80%, alpha error of 20% and confidence interval of 95%, 20 pairs (40 patients) are required to be randomized. If we consider a loss of 25% ( $n=10$ ), a total sample of 50 patients would be required.

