## **SCHEDULE OF ACTIVITIES 2022-2023**

ACTIVITIES	APRIL MAY	JUNE JULY	AGO SEP	OCT NOV	DIC ENE	FEB MARCH	APRIL MAY	JUN JUL	AGO SEP
Elaboration and approval of the research project	X								
Elaboration of placebo		X							
Patient recruitment - Medical and nutritional evaluation. - Initial laboratory studies - Nutritional counseling to establish a Mediterranean style dietary plan. - Initial FibroScan® study			X	X	X				
Medical and nutritional follow-up and monitoring (12 weeks) - Monitoring of compliance with the nutritional plan and treatment. - Laboratory studies - FibroScan® study					X	X	X		

Medical and nutritional follow-up and monitoring (24 weeks) - Monitoring of compliance with the nutritional plan and treatment. - Laboratory studies - FibroScan® study						X	X	X	
Data processing								X	
Statistical analysis of results								X	
Reporting the results Manuscript writing								X	
Dissemination									X

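### The only allocation mechanism the protocol names, systematic sampling, is a fixed-interval rule and contradicts the declared randomised design

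*Protocol*

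**What the plan says.** Section 3 of the protocol, Randomization by groups, is the only place that says how a patient reaches a group: "Patients will be randomly distributed by systematic sampling into 2 groups (A and B". It then describes what each group receives.

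Three other sections treat the trial as randomised:

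- Research Design: "Randomized, controlled, double-blind clinical trial".
- Sample size calculation: "20 pairs (40 patients) are required to be randomized", raised for losses so that "a total sample of 50 patients would be required".
- Interventions: patients are "randomly distributed in a 1:1 ratio to receive the two treatment regimens". This gives the ratio but not the mechanism.

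No section mentions a random number list, computer generation, blocks or concealment, and none gives systematic sampling a special meaning.

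**The concern.** Systematic sampling is a way of drawing a sample from an ordered list at a fixed interval. Used to assign treatment, it leaves at most one chance event, the starting point. After that, position in the order determines every assignment. Such a scheme is usually called quasi-random, and it is not what a randomised trial means by random allocation.

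This is more than detail left to another document. The protocol does name a mechanism, and that mechanism contradicts its own design. A statistical analysis plan that specified a proper random list would conflict with this sentence.

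Two things are at stake. The first is predictability: if one assignment becomes known, for example through an unblinding, the remainder may follow from the enrolment order. That would open a route to selective enrolment and weaken the double blind. The second is the basis for inference: the planned tests could still be computed, but random assignment would no longer justify them.

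**Working it through.** The protocol gives no figure for this point, so there is none to reproduce. The check has three steps: compare the statements, ask what a literal reading implies, and illustrate how predictable the result would be.

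**1. The statements side by side.** Research Design, Sample size calculation and Interventions all say the allocation is random, and none says how. Section 3 says how, and names a fixed-interval method. Nothing elsewhere overrides it.

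**2. What a literal reading implies.** Inputs: 1:1 ratio (Interventions); 50 patients, or 40 before the allowance for losses (Sample size calculation). Equal arms are therefore 25 or 20.

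- Interval k = N/n = 50/25 = 2, and 40/20 = 2. Taken literally, every second patient goes to the same arm.
- The order would most naturally be enrolment order. Patients come from a clinic: "Patients regularly attending the outpatient clinic of the Gastroenterology Department". In the Schedule of Activities, the row "Patient recruitment - Medical and nutritional evaluation" is marked in three two-month columns, August to January. The row "Medical and nutritional follow-up and monitoring (12 weeks" is first marked in the last of these. Treatment thus starts before recruitment ends, so there is no complete list of patients to sample from.

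**3. Predictability, if the rule is alternation (50 patients, 1:1).**

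*Nothing known, random start.* The guesser is entirely right or entirely wrong: (50 + 0)/2 = 25 of 50 (50%). There is no gain.

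*One assignment and the enrolment order known.*
- Alternation: 49 of the other 49 (100%).
- Balanced random list: each other patient is in the opposite arm with probability 25/49 = 0.51, so 25 of 49 are expected correct.

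*All earlier assignments known, best guess each time.* For a balanced list of 2m patients, the expected number correct is m + (2^(2m)/C(2m,m) − 1)/2.

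| Scheme | Calculation | Correct of 50 |
|---|---|---|
| Alternation | 0.5 + 49 | 49.5 (99%) |
| Random list, 25/25 (m = 25) | 25 + (2^50/C(50,25) − 1)/2 | 28.95 (58%) |
| Fixed blocks of 6 (4.1 per block) | 8 × 4.1 + 0.5 + 3/5 | 33.9 (68%) |
| Fixed blocks of 4 (2.833 per block) | 12 × 2.833 + 0.5 + 2/3 | 35.2 (70%) |

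**Number of possible sequences.** Alternation with a random start has 2; a balanced random list has C(50,25) = 1.26 × 10^14. With only 2 equally likely sequences, a test based on the assignment itself cannot give a p-value below 1/2, whereas Analysis of the results sets the threshold at 0.05.

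**The case against.** The strongest reply is that this is a translation slip. The section heading, the sentence itself and three other sections all say random, and the English is loose elsewhere, so one odd term should not turn the trial into a quasi-randomised one. That reading is possible. It would make the sentence a misnomer, but the sentence would still be wrong and would still be the only description of the method.

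The other replies, and what stands of them:

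- **A random start gives each patient a 1/2 chance of either arm.** True, but the assignments are then completely dependent on one another, and the protocol does not state a random start.
- **An interval of 2 proves nothing, since every two-arm 1:1 trial has N/n = 2.** This stands. The ratio is not independent evidence of alternation; it only shows what fixed-interval sampling would mean here.
- **A list of study numbers or treatment packs could exist before anyone enrols.** Also true, but taking such a list at a fixed interval still gives a deterministic order.
- **The harm requires assignments to become known, which the double blind is meant to prevent.** This stands, and the predictability figures are conditional on it.
- **The tests can be justified by a sampling model instead.** They can, but they would then rest on modelling assumptions and no longer on the design the protocol claims.

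**Conclusion.** The concern holds. The one allocation mechanism in the protocol is not, in its standard meaning, random allocation, and it conflicts with its own sentence and with three other sections. This conclusion rests on the wording alone and is firm.

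The size of the consequence is conditional. If the rule is alternation and assignments leak, predictability rises to between 99% and 100%, against 51% to 70% under the random schemes compared. If the start is random and the blind holds, nothing is gained by guessing. Alternation is an inference, and no amount of bias in the treatment effect is claimed. The point must still be corrected, because the description of the trial as randomised depends on this sentence.

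**What to change.** In section 3 of the protocol, replace the reference to systematic sampling with wording such as: patients will be allocated 1:1 by a computer-generated random sequence (for example, permuted blocks), concealed from the staff who enrol patients until assignment. Any equivalent random and concealed scheme would serve. The description of what Groups A and B receive stays as it is.

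Before allocation starts, the cost is one sentence and one generated list; sample size, visits and measurements do not change. The schedule is dated 2022-2023, so allocation may already be complete. In that case a new list cannot help, and the wording must not describe a method that was not used. The sponsor should then state how patients were actually allocated and, if this was by fixed interval, stop describing the trial as randomised.
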